## Trademarks

The following trademarked products are referenced in the present protocol.

Trademarks of the GSK group of companies

Flu-DQIV, Fluarix Quadrivalent, Fluarix Tetra, Fluarix Tetra, α-RIX-Tetra and Influsplit Tetra **Generic description** 

GSK's quadrivalent seasonal influenza vaccine

## Version history

SAP Version	Approval Date	Protocol Version (Date) on which SAP is Based	Change	Rationale
SAP	29 Jun 2021	Amendment 1 (27 May 2021)	Not Applicable	Original version
Amendment 1	29 Mar 2022	Amendment 2 (17 November 2021)	
 
Blinding strategy detail from the study title has been deleted, as they vary between the lot to lot and co-administration groups.
 
Interim analysis has been removed.
 
Components updated with 2021/22 season Flu strains.
 
	
 
It was identified that the intervention type amongst the co-administration groups can be determined by the blinded site and sponsor staff using available information in the electronic case report forms (eCRF), therefore the blinding strategy was adapted to single-blind design for the co-administration groups.
 
The decision was made to not go forward with the BLA filing for the RSV Maternal vaccine, and as a result, the interim analysis was removed.
 
New information made available on the Flu strains.
 

Amendment 2	09 Jun 2022	Amendment 3 (26 May 2022)	
 
The primary and secondary objectives were modified to evaluate only 3 influenza strains. The A/Victoria/2570/2019 (H1N1) strain will be evaluated as part of the tertiary objectives.
 
The secondary safety objective and its corresponding endpoint related to assessment of safety of RSV maternal vaccine when given alone and co-administered with Flu D-QIV from vaccination up to study end was recategorized as a primary objective.
 
Further clarified the analysis details for COVID infection.
 
	
 
Updated due to issues in validation of A/Victoria/2570/2019 (H1N1) influenza strain.
 
Updated to reflect the change to study's safety assessment plan.
 
A participant is defined as having a suspected, probable or confirmed COVID-19 infection during the first 30 days follow-up period, and after that as having or not having the infection until the study end.
 

## 1. INTRODUCTION

The purpose of this SAP is to describe the planned analyses for RSV MAT-010 (214709). Details of the planned analysis are provided.

### 1.1. Objectives, Estimands and Endpoints

**Table 1 Study objectives, endpoints and estimands**

Objectives	Endpoints/Estimands
Primary	
Safety	
The number and percentage of participants in each group reporting
 
 
• Each solicited administration site AE collected during the 7 days follow-up period (Day 1 to Day 7)
 
• Each solicited systemic events in the 7 days follow-up period
 
• Unsolicited AEs collected during the 30 days follow-up period (Day 1 to Day 30)
 
• SAEs in the 30 days follow-up period (Day 1 to Day 30)
 
• SAEs in the 180 days follow-up period (Day 1 to Day 181)
 

Immunogenicity	
RSVPreF3 IgG ELISA concentration at Day 31 (30 days post administration)
 
Measured by ratio of Geometric mean concentration (GMC) between lots in terms of RSVPreF3 IgG ELISA titers at Day 31 (30 days post administration)
 
Flu D-QIV antibody titers against 3 influenza strains at Day 31 (30 days post administration)
 
Measured by ratio of Haemagglutinin inhibition (HI) GMT between group of Flu D-QIV vaccine co-administered with RSVPreF3 vaccine and Flu D-QIV vaccine alone group against 3 strains at Day 31 (30 days post administration)

Secondary	
Confirmatory Immunogenicity**	

 
• To demonstrate the non-inferiority of RSVPreF3 vaccine co-administered with Flu D-QIV compared to given alone based on GMT of RSV A neutralizing antibody at Day 31 post administration
 
• To demonstrate the non-inferiority of Flu D-QIV vaccine co-administered with RSVPreF3 compared to given alone based on Seroconversion rate (SCR*) of Flu D-QIV HI antibody titers against 3 influenza strains at Day 31 post study intervention
 
	
RSV A neutralizing antibody titers at Day 31 (30 days post administration)
 
Measured by ratio of GMT between group of RSVPreF3 vaccine co-administered with Flu D-QIV and RSVPreF3 vaccine alone (pooled lot 1,2,3) group in term of RSV A neutralizing antibody titers at Day 31 (30 days administration)
 
 
• Seroconversion rate to Flu D-QIV HI antibody titers against the 3 influenza strains at Day 31
 
 
Measured by the difference of proportion of participants achieving seroconversion for HI antibody at Day 31 in the group of Flu D-QIV vaccine co-administered with

Objectives	Endpoints/Estimands
	RSVPreF3 vaccine and the group of Flu D-QIV vaccine alone
Descriptive Immunogenicity	

 
To evaluate the humoral immune response of RSVPreF3 vaccine when given alone and co-administered with Flu D-QIV in terms of RSV A, RSV B neutralizing antibody and RSVPreF3 IgG concentration at Day 1 (prior to the vaccination) and Day 31 (post study intervention).
 
	
 
RSV A, RSV B neutralizing antibody titers and RSV PreF3 IgG concentration at Day 1 and Day 31
 
 
GMT of RSV A and RSV B neutralizing antibody, GMC of RSVPreF3 IgG at Day 1 and Day 31, in the group of RSVPreF3 vaccine co-administered with Flu D-QIV and the group of RSVPreF3 vaccine alone

 
To evaluate the humoral immune response to the Flu D-QIV vaccine when given alone and co-administered with RSVPreF3 vaccine in terms of antibody titers against 3 influenza strains at Day 1 and Day 31
 
	
Flu D-QIV HI antibody titers against the 3 influenza strains at Day 1 and Day 31
 
HI GMT in the 3 influenza strains at Day 1 and Day 31 in the group of Flu D-QIV vaccine co-administered with RSVPreF3 vaccine and the group of Flu D-QIV vaccine alone

 
To evaluate seroprotection rate (SPR) and Seroconversion rate (SCR)* of the Flu D-QIV vaccine when given alone and co-administered with RSVPreF3 vaccine
 
	
Seroprotection rate to Flu D-QIV HI antibody titers against the 3 influenza strains at Day 1 and Day 31
 
Measured by the proportion of participants achieving an HI antibody titer <math>\geq 1:40</math> at Day 1 and Day 31 in the group of Flu D-QIV vaccine co-administered with RSVPreF3 vaccine and the group of Flu D-QIV vaccine alone
 
 
Seroconversion rate to Flu D-QIV HI antibody titers against the 3 influenza strains at Day 31
 
 
Measured by the proportion of participants achieving seroconversion for HI antibody at Day 31 in the group of Flu D-QIV vaccine co-administered with RSVPreF3 vaccine and the group of Flu D-QIV vaccine alone


 
To evaluate the humoral immune response in 3 individual lots of RSVPreF3
 
	
 
RSV A, RSV B neutralizing antibody titers and RSVPreF3 IgG antibody concentrations at pre-vaccination and Day 31
 
 
Geometric mean titer/concentration (GMT/GMC) in term of RSV A, RSV B neutralizing antibody and RSVPreF3 IgG antibody at Day 1 (pre-vaccination) and Day 31 in each of 3 lots of the investigational PreF3 vaccine.

Tertiary	

To demonstrate non-inferiority of Flu D-QIV vaccine when co-administered with RSVPreF3 vaccine compared to Flu D-QIV given alone based on Geometric mean titer (GMT) of Flu D-QIV antibody titers against the A/Victoria/2570/2019 (H1N1) influenza strain at Day 31 post administration
	
Flu D-QIV antibody titers against the A/Victoria/2570/2019 (H1N1) influenza strain at Day 31 (30 days post administration)
 
Measured by ratio of Haemagglutinin inhibition (HI) GMT between group of Flu D-QIV vaccine co-administered with RSVPreF3 vaccine and Flu D-QIV vaccine alone group against the A/Victoria/2570/2019 (H1N1) strain at Day 31 (30 days post administration)

To demonstrate the non-inferiority of Flu D-QIV vaccine co-administered with RSVPreF3 compared to given alone based on Seroconversion rate (SCR) of Flu D-QIV HI antibody titers against the A/Victoria/2570/2019 (H1N1) influenza strain at Day 31 post study intervention
	
 
Seroconversion rate to Flu D-QIV HI antibody titers against the A/Victoria/2570/2019 (H1N1) influenza strain at Day 31
 

**CONFIDENTIAL**

[figure not shown]
Objectives	Endpoints/Estimands
	Measured by the difference of proportion of participants achieving seroconversion for HI antibody at Day 31 in the group of Flu D-QIV vaccine co-administered with RSVPreF3 vaccine and the group of Flu D-QIV vaccine alone
To evaluate the humoral immune response to the Flu D-QIV vaccine when given alone and co-administered with RSVPreF3 vaccine in terms of antibody titers against the A/Victoria/2570/2019 (H1N1) influenza strain at Day 1 and Day 31	
Flu D-QIV HI antibody titers against the A/Victoria/2570/2019 (H1N1) influenza strain at Day 1 and Day 31
 
HI GMT in the A/Victoria/2570/2019 (H1N1) influenza strain at Day 1 and Day 31 in the group of Flu D-QIV vaccine co-administered with RSVPreF3 vaccine and the group of Flu D-QIV vaccine alone

To evaluate seroprotection rate (SPR) and Seroconversion rate (SCR) of the Flu D-QIV vaccine when given alone and co-administered with RSVPreF3 vaccine	
 
• Seroprotection rate to Flu D-QIV HI antibody titers against the A/Victoria/2570/2019 (H1N1) influenza strain at Day 1 and Day 31
 
 
Measured by the proportion of participants achieving an HI antibody titer <math>\geq 1:40</math> at Day 1 and Day 31 in the group of Flu D-QIV vaccine co-administered with RSVPreF3 vaccine and the group of Flu D-QIV vaccine alone
 
 
• Seroconversion rate to Flu D-QIV HI antibody titers against the A/Victoria/2570/2019 (H1N1) influenza strain at Day 31
 
 
Measured by the proportion of participants achieving seroconversion for HI antibody at Day 31 in the group of Flu D-QIV vaccine co-administered with RSVPreF3 vaccine and the group of Flu D-QIV vaccine alone

CCI

\* The SCR is defined as the proportion of participants with:  
 A Day 1 (pre-vaccination) serum anti-HI titer  $<1:10$  and a Day 31 (post-vaccination) serum anti-HI titer  $\geq 1:40$ , or  
 A Day 1 (pre-vaccination) serum anti-HI titer  $\geq 1:10$  and a fold increase (post/pre)  $\geq 4$  at Day 31

\*\* Two confirmatory objectives will be tested sequentially.

## 1.2. Study Design

Overview of Study Design and Key Features	

Randomization 3:3:2:2:2:6 N=1541
  
The diagram illustrates the study timeline across three visits. Visit 1 (Day 1) includes screening (RSV1, RSV2, RSV3, RSV+Flu pooled, RSV1+Flu, RSV2+Flu, RSV3+Flu, Flu+P), a blood sample, and a urine pregnancy sample. Visit 2 (Day 31) includes Flu SoC**. Visit 2 (Day 181) includes TC2. The timeline also shows 7-day and 30-day intervals for administration site and systemic solicited events, and unsolicited AEs. SAEs and pregnancies are tracked throughout the entire study period. A vaccination phase and follow-up phase are indicated at the bottom.
	

SOC=Standard of Care * Screening and vaccination will happen on Visit 1(Day 1). The blood sample collection must be collected before administering the vaccine(s). ** Visit 2 Flu D-QIV vaccinations are not part of experimental design. It serves as an optional vaccination for the participant to decide if they would like to get the vaccination as part of their standard of care. The blood sample collection must be collected before administering the Flu D-QIV vaccine.
	
Design Features	
 
Study Phase and Population: Phase III, Non-pregnant women
 
Design type: Randomized, Parallel, multi-country study
 
Control type: Placebo controlled, Saline (NaCl) solution
 
Study duration: The study vaccine will be administered at Visit 1 and the participant will be followed for 6 months until the study conclusion.
 
Blinding: This study will utilize an observer-blind manner to evaluate the lot-to-lot consistency of GSK RSVPreF3 vaccine and single-blind manner to evaluate the immune response, safety and reactogenicity of RSV maternal vaccine when co-administered with GSK quadrivalent influenza. Detailed blinding design is described in Protocol Section 6.3.5
 

Overview of Study Design and Key Features	
Study intervention	Study (intervention) groups are described in Table 2
Study intervention Assignment	Approximately 1541 participants will be randomized into 7 study groups (5 main study groups including 1 pooled group [RSV1+Flu, RSV2+Flu, RSV3+Flu]) with randomization ratio of RSV1:RSV2:RSV3: RSV1+Flu: RSV2+Flu: RSV3+Flu: Flu+P as 3:3:3:2:2:2:6. An automated internet based system (SBIR) will be used to randomly allocate a study group and treatment number to each participant. Age (18-32 vs. 33-49) and center will be minimization factors. Minimization factors will have equal weight in the algorithm.

**Table 2 Study groups and intervention**

Study groups	Approximate number of participants	Age (Min-Max)	Study intervention	Standard of Care Vaccination*
RSV1	220	18 – 49 years	RSV MAT 120 (Lot1)	Flu D-QIV
RSV2	220	18 – 49 years	RSV MAT 120 (Lot2)	Flu D-QIV
RSV3	220	18 – 49 years	RSV MAT 120 (Lot3)	Flu D-QIV
RSV1+Flu	147	18 – 49 years	RSV MAT 120 (Lot 1) Flu D-QIV	
RSV2+Flu	147	18 – 49 years	RSV MAT 120 (Lot 2) Flu D-QIV	
RSV3+Flu	147	18 – 49 years	RSV MAT 120 (Lot 3) Flu D-QIV	
Flu+P	440	18 – 49 years	Flu D-QIV placebo	

RSV MAT 120 =RSVPreF3 vaccine

\*Standard of care vaccine administered only to ensure the participants receive the standard of care.

## 2. STATISTICAL HYPOTHESES

The study includes 2 confirmatory co-primary objectives:

- To demonstrate the lot-to-lot consistency of 3 lots of RSVPreF3 vaccine in terms of geometric mean concentration (GMC) of RSVPreF3 IgG ELISA at Day 31.

### Null hypothesis vs. Alternative hypothesis:

$H_0$ : at least one of the two-sided 95% confidence intervals for the 3 pair-wise GMC ratios between 2 lots are outside the range of 0.67 to 1.5

$H_a$ :  $0.67 < \mu_{\text{lot1}} / \mu_{\text{lot2}} < 1.5$  and  $0.67 < \mu_{\text{lot1}} / \mu_{\text{lot3}} < 1.5$  and  $0.67 < \mu_{\text{lot2}} / \mu_{\text{lot3}} < 1.5$

where  $\mu$  represents the GMC of RSVPreF3 IgG at Day 31 from each lot. The lot-to-lot consistency will be demonstrated if two-sided 95% confidence intervals for the 3 pair-wise GMC ratios at Day 31 falls within 0.67 and 1.5.

- To demonstrate the non-inferiority of Flu D-QIV vaccine when co-administered with RSVPreF3 vaccine as compared to Flu D-QIV vaccine administered alone in terms of geometric mean titer (GMT) of Flu D-QIV HI antibody against the 3 influenza strains (A/Tasmania/503/2020 (H3N2) IVR-221, B/Washington/02/2019, and B/Phuket/3073/2013) at Day 31.

**Null hypothesis vs. Alternative hypothesis:**

$$H_0: \mu_{\text{co-ad group}} / \mu_{\text{alone}} \leq 0.67 \text{ vs } H_a: \mu_{\text{co-ad group}} / \mu_{\text{alone}} > 0.67$$

where  $\mu$  represents the GMT of Flu D-QIV HI antibody at Day 31. The non-inferiority will be demonstrated if the lower limits of the two-sided 95% CI on the GMT ratio (co-ad group RSV+Flu with 3 lots pooled divided by Flu+P group) is greater than 0.67 at Day 31 post vaccination for all the 3 strains (A/Tasmania/503/2020 (H3N2) IVR-221, B/Washington/02/2019, and B/Phuket/3073/2013).

In addition, the study also includes 2 confirmatory secondary objectives. These hypothesis tests will be conducted sequentially only if the primary objective of non-inferiority of Flu D-QIV vaccine when co-administered with RSVPreF3 vaccine as compared to Flu D-QIV vaccine administered alone is met.

- To demonstrate the non-inferiority of RSVPreF3 vaccine when co-administered with Flu D-QIV vaccine as compared to RSVPreF3 vaccine administered alone in terms of GMT of RSV A neutralizing antibody at Day 31.

**Null hypothesis vs. Alternative hypothesis:**

$$H_0: \mu_{\text{co-ad group}} / \mu_{\text{alone}} \leq 0.67 \text{ vs } H_a: \mu_{\text{co-ad group}} / \mu_{\text{alone}} > 0.67$$

where  $\mu$  represents the GMT of RSV A neutralizing antibody at Day 31. The non-inferiority will be demonstrated if the lower limits of the two-sided 95% CI on the GMT ratio (co-ad group RSV+Flu divided by RSV alone group with 3 lots pooled in both groups) is greater than 0.67 at Day 31 post vaccination.

- To demonstrate the non-inferiority for each strain (A/Tasmania/503/2020 (H3N2) IVR-221, B/Washington/02/2019, and B/Phuket/3073/2013) of Flu D-QIV vaccine when co-administered with RSVPreF3 vaccine as compared to Flu D-QIV vaccine administered alone in terms of seroconversion rate (SCR) at Day 31.

**Null hypothesis vs. Alternative hypothesis:**

$$H_0: p_{\text{alone}} - p_{\text{co-ad group}} \geq 10\% \text{ vs } H_a: p_{\text{alone}} - p_{\text{co-ad group}} < 10\%$$

where  $p$  represents the SCR for each influenza strain at Day 31. The non-inferiority for each strain will be demonstrated if the upper limits of the two-sided 95% CI on the SCR difference (Flu+P group minus co-ad group RSV+Flu with 3 lots pooled) is less than 10% at Day 31 post vaccination.

## 2.1. Multiplicity Adjustment

To ensure the global type I error for the primary objectives is controlled at 5%, each of the primary objectives will be tested using a nominal one-sided alpha of 2.5%.

If the primary objective of non-inferiority of Flu D-QIV in terms of GMT is met, the secondary confirmatory objective of non-inferiority of RSVPreF3 vaccine in terms of GMC will be tested at alpha of 2.5%, if this objective is met, the non-inferiority of Flu D-QIV in terms of SCR will be tested at alpha of 2.5% for each strain, otherwise, it will not be tested.

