# 9.2.3. Secondary objectives

To control the global type I error, a hierarchical procedure will be used for confirmatory objectives assessment.

For instance, the secondary objective to demonstrate the non-inferiority of RSV A neutralizing antibodies using GMT ratios can only be assessed if the primary objective assessing the non-inferiority of GMT ratio for Flu D-QIV strains is met. As per the hierarchical procedure, secondary objective assessing the non-inferiority based on SCR difference of Flu D-QIV will only be assessed if the non-inferiority of RSV A neutralizing antibodies using GMT ratios is met.

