#### **4.3. Secondary Endpoint(s) Analyses**

### 4.3.1. Immunogenicity analysis

#### 4.3.1.1. Secondary confirmatory analysis

In order to control the global type I error, the objectives will be assessed sequentially.

- Non-inferiority of RSVPreF3 vaccine co-administered with Flu D-QIV vaccine as compared to RSVPreF3 vaccine administered alone in terms of RSV A neutralizing antibody titers at Day 31

The GMT ratio and its two-sided 95% CI between 2 groups (RSV+Flu group with 3 lots pooled divided by RSV alone group with 3 lots pooled) will be computed by exponentiating the mean difference and its 95% CI on log10 transformed scale estimated from t-distribution.

Summary table will show for each group the number of observations included in the calculation and GMT value, and between group GMT ratio with corresponding 95% CI.

No interference on RSVPreF3 vaccine from quadrivalent seasonal influenza vaccine (Flu D-QIV) will be demonstrated if lower bound of the two-sided 95% CI of GMT ratio is above 0.67.

- Non-inferiority for each of the 3 strains of Flu D-QIV vaccine when co-administered with RSVPreF3 vaccine as compared to Flu D-QIV vaccine administered alone at Day 31 in terms of Seroconversion rate (SCR)

The SCR difference and its two-sided 95% CI between 2 groups (Flu+P group minus RSV+Flu group with 3 lots pooled) will be calculated for each strain (A/Tasmania/503/2020 (H3N2) IVR-221, B/Washington/02/2019, and B/Phuket/3073/2013) at Day 31. 95% CI calculation will be based on Miettinen and Nurminen confidence interval [Miettinen, 1985].

Summary table will show for each group the number of observations included in the calculation, number and percentage of seroconverted participants, and between group SCR difference with corresponding 95% CI.

For each strain, non-inferiority will be demonstrated if the upper bound of the two-sided 95% CI is less than 10% at Day 31 post vaccination.

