The criteria to evaluate non-inferiority with respect to the SCR difference for Flu D-QIV antibody titers against 3 influenza strains is that the upper limits of the 95% CI on the SCR difference (Flu+P group minus RSV+Flu) is less than the pre-defined clinical limit of 10% at Day 31 post vaccination.

With the assumptions of SCR for the reference group as indicated in [Table 10](#), significance level 0.025, non-inferiority margin 10%, 400 evaluable participants (10% non-evaluable rate) provides at least 80% power to conclude non-inferiority for each strain ([Table 10](#)).

**Table 10 Powers to demonstrate non-inferiority in terms of HI antibody SCR for Flu D-QIV strains between Flu D-QIV vaccine co-administered with RSVPreF3 vaccine and administered alone at Day 31 post vaccination**

Endpoint	NI criteria	Anticipated SCR*	Number of participants per group (evaluable)	Power
B/Washington/02/2019 SCR	10%	65%	400	84.39%
A/Tasmania/503/2020 (H3N2)** IVR-221 SCR	10%	65%	400	84.39%
B/Phuket/3073/2013 SCR	10%	65%	400	84.39%

By Pass 2019, Non-Inferiority Tests for the difference between two proportions, alpha=2.5%

\*SCR used in the reference group for power calculation is from Study Tdap-0.3-008, Suppl. Table 36.

\*\*A/Tasmania/503/2020 (H3N2) IVR-221 (an A/Cambodia/e0826360/2020 (H3N2)-like virus).

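### The last confirmatory step tests seroconversion rate separately for three strains at one-sided 2.5% with no all-strain rule, so the claimed sequential error control is not guaranteed

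*SAP*

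**What the plan says.** Three confirmatory steps are chained: Flu D-QIV GMT, then RSV A GMT, then Flu D-QIV seroconversion rate (SCR).

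- **Error-control claim.** Protocol 9.2.3: "To control the global type I error, a hierarchical procedure will be used for confirmatory objectives assessment". SAP 4.3.1.1: "In order to control the global type I error, the objectives will be assessed sequentially".
- **Level at the SCR step.** SAP 2.1: "the non-inferiority of Flu D-QIV in terms of SCR will be tested at alpha of 2.5% for each strain".
- **SCR success rule.** SAP 2: "The non-inferiority for each strain will be demonstrated if the upper limits of the two-sided 95% CI on the SCR difference" is below 10%. SAP 4.3.1.1: "For each strain, non-inferiority will be demonstrated if the upper bound of the two-sided 95% CI is less than 10" %. Protocol 9.4.2 also works strain by strain.
- **GMT success rule, for contrast.** SAP 2 requires that the lower confidence limit "is greater than 0.67 at Day 31 post vaccination for all the 3 strains".
- **Wording that treats SCR as one objective.** The footnote to SAP Table 1 says "Two confirmatory objectives will be tested sequentially". SAP 5.3.2 gives a single criterion "with respect to the SCR difference for Flu D-QIV antibody titers against 3 influenza strains is that the upper limits of the 95% CI".
- **Power.** Protocol Table 17 and SAP Table 10 give 84.39% for each strain. Protocol Table 15 and SAP Table 8 add a global power row for GMT (95.68%); the SCR tables have none.

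**The concern.** A fixed sequence keeps the error rate at 2.5% when each step yields a single decision made at that level. The GMT step holds three tests but qualifies, because all three must succeed. The SCR step, as its decision rules are written, yields three separate decisions at full alpha.

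The plan therefore supports two success rules. Under the strain-by-strain rule, the report could claim confirmatory SCR non-inferiority for one or two strains after the others fail, without the error protection that the plan asserts. Under an all-strain rule, error is controlled, but the chance of meeting the objective is lower than the only power figure shown. If the choice is left open, it could be made after seeing which strains passed.

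**Working it through.** **Inputs.** From SAP 2.1, 5.3.2 and Table 10: one-sided 2.5% per strain, 400 evaluable per group, reference SCR 65%, margin 10 points. A true difference of zero is an assumption; it is not stated for SCR, but it reproduces the plan's power.

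**1. The plan's own figure.** SE = √(2 × 0.65 × 0.35 / 400) = 0.0337. Power = Φ(0.10/0.0337 − 1.96) = Φ(1.005) = 84.3%. With the Miettinen-Nurminen score test it is 84.4%. The stated 84.39% reproduces.

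**2. Strain-by-strain rule, earlier steps passed.** The exact size of one Miettinen-Nurminen test at 65% versus 55% is 2.49%.

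- Three true nulls, independent strains: 1 − (1 − 0.0249)³ = 7.3%. The bound under any dependence is 3 × 2.5% = 7.5%.
- Two true nulls, independent: 1 − (1 − 0.0249)² = 4.9%.
- Between-strain correlations are not in the documents. At assumed values of 0.3, 0.5 and 0.7, three true nulls give 6.8%, 6.3% and 5.5%. For two, the figure runs from 4.8% at 0.3 to 4.2% at 0.7.

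**3. Counting the GMT test that comes first.** SCR is reached only if all three GMT lower limits exceed 0.67. This was simulated (400,000 runs) with GMT SD 0.6 on the log10 scale, an assumed within-strain correlation of 0.5 between the GMT and SCR statistics, and RSV A taken as always passed (its stated power is 99.99%). A fall from 65% to 55% is a shift of Φ⁻¹(0.65) − Φ⁻¹(0.55) = 0.385 − 0.126 = 0.26 fold-rise SDs, so a pure location shift gives a GMT ratio of 10^(−0.26 × SD). The fold-rise SD is also not in the documents.

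| Scenario | GMT ratio | Chance of any false SCR claim (correlations 0.3–0.7) |
|---|---|---|
| Mean titers unchanged | 1.00 | 5.4%–6.7% |
| Common shift, fold-rise SD 0.3 | 0.84 | 3.8%–4.3% |
| Common shift, fold-rise SD 0.4 | 0.79 | 1.8%–2.9% |
| Common shift, fold-rise SD 0.6 | 0.70 | under 0.5% |

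**4. All-strain rule.** The step stays at 2.5% or less. Joint power:

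- Independent strains: 0.8439³ = 60.1%.
- Assumed correlations 0.3, 0.5, 0.7: 64.7%, 68.2%, 72.2%.
- By the plan's apparent convention: the GMT global power equals 1 − 3(1 − 0.9856) = 95.68%. The same formula for SCR gives 1 − 3(1 − 0.8439) = 53.2%, a lower bound under any dependence.

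**The case against.** The strongest reply is that all three strains were meant. SAP 2 states one SCR objective and names the three strains, and the objectives table counts two confirmatory secondary objectives, not four. On that reading there is no alpha problem. This has force as evidence of intent, but the sentences that define success are per strain, and the same sections spell out an all-strain rule for GMT. The plural used for the SCR limits in SAP 5.3.2 settles nothing, because the plan also uses the plural for the single RSV A comparison.

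The second reply is that 7.3% is not the error rate of the whole procedure, since SCR comes from the same HI titers as the GMT that must pass first. This stands as a limit on size. Unchanged mean titers with a 10-point SCR fall would, under a normal fold-rise model, need the fold-rise SD to be about three times as large in the co-administration group (0.385/0.126 = 3.1). Under a common shift the range straddles 2.5%. What remains is that no document links SCR loss to a mean shift, so the gate does not guarantee control.

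It is also true that SCR comes last, so no later claim inherits the error; that 84.39% is correctly labelled per strain; and that every strain's difference and interval will be tabulated. Enrolment was complete by Protocol Amendment 3, so a joint power figure cannot change the sample size.

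**Conclusion.** The concern holds. As written, the SCR step allows three separate confirmatory claims at one-sided 2.5% each, and sequential testing alone does not deliver the stated error control for them. The worst case, conditional on passing the earlier steps, is 7.3% for independent strains (bound 7.5%). With the GMT test counted, the simulated scenarios run from under 0.5% to 6.7%, depending on correlations and a fold-rise SD that the plan does not give. Material inflation is therefore possible but not established.

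On the all-strain reading there is no inflation, and the gap is an unstated joint power of 53% to 72% in the cases examined. The GMT, RSV A, lot-consistency and safety conclusions are unaffected. It should be fixed, because it determines what may be claimed at a step labelled confirmatory.

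**What to change.** In SAP 2, 2.1 and 4.3.1.1 and in Protocol 9.4.2, state that the SCR objective is met only if the upper 95% limits for all three strains are below 10%. Each test stays at 2.5%, and so does the step. While editing, align Protocol 9.4.2, which accepts a limit equal to 10%, with the strict inequality in Protocol 9.2.3.2 and the SAP.

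A global power row in Protocol Table 17 and SAP Table 10, with its assumption (about 53% as a lower bound, 60% if independent), would match the GMT tables. It is desirable rather than essential.

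If separate strain claims are wanted, pre-specify Holm or a fixed strain order instead.

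The cost is a sentence in each section and a less favourable stated power. The all-strain rule gives up stand-alone strain claims. Holm keeps them, but its first step, at 2.5%/3 = 0.83%, has about 72% power per strain against 84%. No additional participants or procedures are needed. The choice must be made before results are seen.
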